### 11.3 Analysis Sets

For the purposes of analysis, the following populations are defined:

Population	Description
ITT Population	All patients who are randomized. Patients are grouped within the ITT population according to the treatment to which they are randomized. This is the primary analysis set for baseline characteristics and efficacy endpoints unless otherwise specified.
Safety Population	All patients who receive $\geq 1$ dose (or partial dose) of study drug. Patients are grouped according to the treatment they actually receive. This is the primary analysis set for all safety analyses and drug administration.
PK Population	All patients in the safety population who have evaluable analyte concentration-time profiles that allow for computation of meaningful PK parameter values.
Immunogenicity Population	All patients in the safety population with baseline and $\geq 1$ post-baseline immunogenicity assessment.
HRQoL Population	All patients in the ITT population who have a baseline and $\geq 1$ post-baseline assessment (defined for each instrument).

Abbreviations: HRQoL = health-related quality of life; ITT = intent-to-treat; PK = pharmacokinetic

### 11.4 Demographics and Baseline Characteristics

A description summary of demographics and key baseline characteristics will be provided. Details will be included in the SAP.

### 11.5 Efficacy Analyses

#### 11.5.1 Primary Efficacy Analyses

ORR is defined as the percentage of patients with a confirmed best overall response of CR or PR by RECIST 1.1 per BICR in the ITT population. As a primary efficacy endpoint, ORR will be tested at an overall alpha level of 0.001. The Cochran Mantel Haenszel (CMH) test statistic will

be used to compare the proportion of patients with an objective response between the 2 treatment arms.

The ORR difference between the two treatment arms with its 95% and 99.5% confidence intervals (CIs) will be calculated by the CMH test statistic using the normal approximation. The ORR and its corresponding 95% exact CI will also be calculated by Clopper-Pearson method for each arm. Patients who do not have on-study tumor assessments to evaluate response status will be counted as non-responders.

Overall survival (OS) is defined as the time between the date of randomization and the date of death due to any cause. A patient who does not have a date of death will be censored on the last date for which the patient was known to be alive.

As another primary efficacy endpoint, OS will be evaluated at an overall alpha level of 0.049 if ORR is not significant and at 0.05 if ORR is significant. The regular stratified log-rank test will be used at IA2 to compare overall survival between the two treatment arms. At the final analysis, the weighted combination version of the stratified log-rank test with prespecified weights (Lehmacher 1999) will be used to compare overall survival between the two treatment arms. A stratified Cox proportional hazards model with treatment as the single covariate will be used to estimate the hazard ratio and corresponding 95% CI. The weighted combination approaches as specified in Brannath et. al. (Brannath 2006) will be performed as an exploratory analysis. The Kaplan-Meier method will be used to summarize overall survival per arm, including Kaplan-Meier curves, medians with corresponding 95% CIs, etc.

At the first interim analysis, ORR will be assessed for futility: ORR futility assessment (ie, the difference in ORR proportions is  $\geq 0\%$  [bempegaldesleukin plus pembrolizumab minus pembrolizumab monotherapy]) will serve as a gate to proceed to the Phase 3 portion of the study.

If the DMC determines that the study should continue based on the prespecified futility boundary, Phase 3 of the study will begin following a projected 4-month enrollment pause for the first interim analysis readout. At the second interim analysis when approximately 500 patients have been randomized and about 231 overall survival events have been observed, the following tests will be conducted:

- ORR will be tested at a statistical significance level of 0.001 at the second interim analysis.
- If ORR is not significant at the second interim analysis, overall survival will be tested at an overall alpha level of 0.049 and at  $\alpha = 0.021$  at the second interim analysis.
- If ORR is significant at the second interim analysis, the fallback method will be used, and overall survival will be tested at an overall alpha level of 0.05 and at  $\alpha = 0.022$  at the second interim analysis.

At the final analysis, the primary analysis of overall survival to claim statistical significance will be based on the weighted combination version of the stratified log-rank test with prespecified

weights (Lehmacher 1999). Statistical significance level for the final analysis is 0.043 or 0.044 depending on whether ORR is significant at the second interim analysis. Prespecified weights for the primary OS are  $w = \sqrt{231/345}$  and  $1-w$  for events occurring before and after the second interim analysis, respectively. The middle point, 345, of minimum and maximum event sizes is chosen to set up the weights. The conventional stratified log-rank test with equal weights for every patient will be conducted as a sensitivity analysis. Details will be provided in the SAP.

### 11.5.2 Secondary Analyses

**Progression-free survival (PFS):** defined as the time between the date of randomization and the first date of documented disease progression using RECIST 1.1 per BICR or death due to any cause, whichever comes first. Stratified log-rank test will be used to compare PFS between the two treatment arms. PFS will be tested following OS significance and at the same significant level as OS. A stratified Cox proportional hazards model with treatment as the single covariate will be used to estimate the hazard ratio and corresponding 95% CI for PFS. The Kaplan-Meier method will be used to summarize PFS, including Kaplan-Meier curves, medians with corresponding 95% CIs, etc.

The censoring rules for PFS will be detailed in the SAP.

[REDACTED]

[REDACTED]

[REDACTED]

[REDACTED]

[REDACTED]

[REDACTED]

[REDACTED]

[REDACTED]

### 11.9.1 Pharmacokinetic Analyses

Plasma concentrations of bempegaldesleukin-related molecules and serum concentrations of pembrolizumab will be measured using validated or qualified method(s).

PK concentrations will be summarized using summary statistics. PK concentrations from this study will be combined with data from other studies to conduct population PK analyses. Model predicted exposures may be used for exposure-response analyses of selected efficacy and safety endpoints. If the analyses are conducted, the results of population PK analyses and exposure-response analyses will be reported separately from the Clinical Study Report of this study.

### 11.9.2 Immunogenicity Analyses

Incidence of anti-drug antibodies (ADA) will be determined by measurements of anti-bempegaldesleukin, anti-interleukin-2 (anti-IL-2), anti-polyethylene glycol, and anti-pembrolizumab antibodies. Validated methods will be used for the ADA measurements. Immunogenicity will be reported for ADA positive status and ADA negative status, relative to baseline. Presence of neutralizing antibody may be reported, if applicable. Effect of immunogenicity on safety/efficacy and PK may be explored.

### 11.9.3 Patient-reported Outcome Analyses

Patient-reported outcome (PRO) questionnaires, EORTC QLQ-C30 and EORTC QLQ-H&N35, will be administered by trained site personnel and completed by patients at baseline and throughout the study. It is a best practice and strongly recommended that PROs are administered to randomized patients prior to study drug administration, AE evaluation, and disease status notification.

Global health status/quality of life assessment is based on the global health status/quality of life scales of the EORTC QLQ-C30 (items 29 and 40); pain is based on the pain multi-item scales of the EORTC QLQ-H&N35 (items 31 to 34), and time to deterioration in swallowing (ie, the time from baseline to first onset of PRO deterioration with confirmation), is based on the swallowing multi-item scales of the EORTC QLQ-H&N35 (items 35 and 38). The deterioration in the global health status/quality of life, pain, and swallowing endpoints is defined as a 10 points or greater worsening from baseline for each multi-item scale (Bjordal 2000; Osoba 1998; King 1996) and confirmed by a second adjacent 10 points or more deterioration from baseline under a right-censoring rule.

**Time to PRO deterioration in global health status/quality of life:** defined as time from baseline to the first onset of PRO deterioration with confirmation at the next visit for the global health status/quality of life assessment based on the global health status/quality of life scales of the European Organization for Research and Treatment of Cancer (EORTC) Quality of Life Questionnaire-Core 30 (QLQ-C30).

**Time to PRO deterioration in pain:** defined as time from baseline to the first onset of PRO deterioration with confirmation for pain based on the pain multi-item scales of EORTC QLQ head and neck cancer specific module (EORTC QLQ-H&N35).

**Time to PRO deterioration in swallowing:** defined as time from baseline to the first onset of PRO deterioration with confirmation for swallowing based on the swallowing multi-item scales of EORTC QLQ-H&N35.

For the above three time to PRO deterioration endpoints, the stratified log-rank test will be used to compare the two treatment arms. A stratified Cox proportional hazards model with treatment as the single covariate will be used to estimate the hazard ratio and corresponding 95% CI, and the Kaplan-Meier method will be used to summarize these time-to-event endpoints per arm, including Kaplan-Meier curves, medians with corresponding 95% CIs, etc.

**Mean change from baseline in global health status/quality of life:** defined as mean changes from baseline in global health status/quality of life assessment based on the global health status/quality of life scales of EORTC QLQ-C30.

To assess the treatment effects on the PRO score changes from baseline in the global health status/quality of life outcome, a constrained longitudinal data analysis (cLDA) model will be applied, with the PRO score as the response variable, and treatment by time interaction, and stratification factors as covariates. Treatment effect on PRO score change from baseline will be primarily evaluated at Week 12. The differences in the least square mean change from baseline will be reported at the primary analysis time point.

Additionally, mean change from baseline in global health status/quality of life will be summarized by visit and the graphs for the mean changes across visits will be provided.

**Changes from baseline in HR-QoL assessments:** Change from baseline in health-related quality-of-life (HR-QoL) assessed by EORTC QLQ-C30 and the EORTC QLQ-H&N35 will be summarized by visit and graphs for mean changes by visit will be provided.

**Opioid analgesic use:** will be measured based on reported concomitant medications. Opioid analgesic use will be summarized descriptively and the mean opioid analgesic use and change from baseline will be plotted across visits.

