### 4.2 Secondary Objectives and Endpoints

The secondary objectives and endpoints listed below involve comparison of bempegaldesleukin plus pembrolizumab versus pembrolizumab monotherapy in first-line patients with recurrent or metastatic HNSCC and positive PD-L1 expression (defined by CPS  $\geq$  1) who have not received prior therapy for the treatment of recurrent or metastatic HNSCC:

Secondary Objective	Endpoint
To compare progression-free survival (PFS).	PFS, defined as the time from randomization to the first documented disease progression (per RECIST 1.1 by BICR) or death due to any cause, whichever occurs first.
To compare time to deterioration in global health status/quality of life, pain, and swallowing.	The time from baseline to a $\geq$ 10-point decrease from baseline with confirmation by the subsequent visit of a $\geq$ 10-point deterioration from baseline in: 
 
Global health status/quality of life assessment based on the global health status/quality of life scales of the European Organization for Research and Treatment of Cancer (EORTC) Quality of Life Questionnaire-Core 30 (QLQ-C30).
 
Pain based on the pain multi-item scales of EORTC QLQ head and neck cancer specific module (EORTC QLQ-H&N35).
 
Swallowing based on the swallowing multi-item scales of EORTC QLQ-H&N35.
 

To compare mean change from baseline in global health status/quality of life.	Mean change from baseline in global health status/quality of life scales of EORTC QLQ-C30.
To compare the overall safety and tolerability.	Safety will be based on assessments of treatment-emergent adverse events (AEs) and serious AEs (SAEs).

[Redacted]

[Redacted]	[Redacted]
[Redacted]	[Redacted]
[Redacted]	[Redacted]
[Redacted]	[Redacted]
[Redacted]	[Redacted]
[Redacted]	[Redacted]
[Redacted]	[Redacted]
[Redacted]	[Redacted]
[Redacted]	[Redacted]
[Redacted]	[Redacted]
[Redacted]	[Redacted]
[Redacted]	[Redacted]
[Redacted]	[Redacted]
[Redacted]	[Redacted]
[Redacted]	[Redacted]
[Redacted]	[Redacted]
[Redacted]	[Redacted]

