### 9.2.2 EORTC QLQ-C30 and EORTC QLQ-H&N35

The EORTC QLQ-C30 ([Aronson 1993](#)) is the most commonly used quality of life instrument in oncology trials. The EORTC QLQ-C30 is composed of multi-item scales and single item measures. These include 5 functional scales (physical, role, emotional, cognitive, and social), 3 symptom scales (fatigue, nausea/vomiting, and pain), a global health status/HRQoL scale, and 6 single items (dyspnea, insomnia, appetite loss, constipation, diarrhea, and financial difficulties). Each of the multi-item scales includes a different set of items – no item occurs in more than one scale.

The EORTC QLQ-H&N35 is in use worldwide as one of the standard instruments for measuring quality of life in head and neck cancer patients ([Mehanna 2006](#); [Tschiesner 2008](#)) and consists of 7 multi-item scales measuring pain in the mouth, problems with swallowing, senses, speech, social eating, social contact, and sexuality, and 11 single-item scales assessing problems with teeth, mouth opening, dry mouth, sticky saliva, coughing, feeling ill, use of analgesics, use of nutritional supplements, use of feeding tube, weight gain, and weight loss ([Bjordal 1999](#); [Bjordal 1994](#)). The EORTC QLQ-C30 and EORTC QLQ-H&N35 are psychometrically and clinically validated instruments appropriate for assessing quality of life in patients with head and neck cancer. These instruments were used in the EXTREME registration trial (NCT00122460) comparing platin-5-fluorouracil alone versus combined with cetuximab as first-line treatment in recurrent or metastatic HNSCC, which led to the FDA approval of cetuximab monotherapy in patients with recurrent or metastatic HNSCC refractory to cisplatin ([Bjordal 2000](#); [Chera 2014](#)). They were also used in the Phase 3 trial of patients with locoregionally advanced head and neck cancer receiving radiotherapy alone or radiotherapy plus cetuximab ([Tschiesner 2008](#)).

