For the global health status/quality of life and function scales, a higher value indicates a better level of function; for symptom scales and items, a higher value indicates increased severity of symptoms. Prior literature indicates that head and neck pain and the ability to swallow are clinically relevant symptom measures in the recurrent or metastatic HNSCC population ([Bjordal 2000](#); [Chera 2014](#); [Mesia 2010](#); [Machiels 2014](#)). Thus, time to deterioration in the pain and swallowing multi-item scales of the EORTC QLQ-H&N35, in addition to time to deterioration and mean change from baseline in global health status/quality of life scale of the EORTC QLQ-C30, will be evaluated as secondary objectives.

Both the EORTC QLQ-C30 and EORTC QLQ-H&N35 use a recall period of the past week.

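### Protocol Section 11.9.3 assigns item 40 to the 30-item QLQ-C30, so the only item list given for the global health scale is wrong as printed

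*Protocol*

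**What the plan says.** Protocol Section 11.9.3 is the only place in the documents that gives item numbers for the patient-reported endpoints. One sentence covers all three scales:

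- Global health: "global health status/quality of life scales of the EORTC QLQ-C30 (items 29 and 40", with the item list in brackets.
- Pain: "pain multi-item scales of the EORTC QLQ-H&N35 (items 31 to 34".
- Swallowing: "swallowing multi-item scales of the EORTC QLQ-H&N35 (items 35 and 38".

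The same section spells out the core instrument as "Quality of Life Questionnaire-Core 30 (QLQ-C30".

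Elsewhere the scales are identified by name alone. Section 4.2 lists one endpoint as "Mean change from baseline in global health status/quality of life scales of EORTC QLQ-C30", and the synopsis does likewise. Section 9.2.2 confirms that two secondary objectives rest on the global health scale: "time to deterioration and mean change from baseline in global health status/quality of life scale of the EORTC QLQ-C30, will be evaluated as secondary objectives".

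Section 11.1 leaves detailed methods to the SAP. The current SAP (Sections 1.0 and 2.0) reports that the trial was discontinued with one patient treated. It replaces all summaries with patient listings and does not name patient-reported outcomes among them.

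**The concern.** A questionnaire named for 30 items should have no item 40, and on the sentence's own numbering 40 falls in the head and neck module. A programmer who took the bracketed list as the scoring rule would combine one core item with one module item and call the result global health.

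Two secondary analyses would inherit that score. One is the stratified log-rank comparison of time to a confirmed worsening of at least 10 points. The other is the longitudinal model of change from baseline, evaluated primarily at Week 12. Neither would then measure the scale named in the objectives. Section 11.9.3 is the analysis text, and nothing else in the protocol or SAP lists the items, so the error cannot be corrected from the documents themselves.

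**Working it through.** No power or alpha figure is involved. The check is whether the printed item numbers are consistent with one another.

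**Inputs, all from Section 11.9.3**

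- Core length: 30, taken from the instrument's name. The documents give no separate count.
- Global health items: 29 and 40.
- Pain items (module): 31 to 34.
- Swallowing items (module): 35 and 38.

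**Step 1: range of each instrument.** A 30-item core occupies numbers 1 to 30. The first module number printed is 31 = 30 + 1, so the module continues the core's numbering. If the 35 in the module's name is its item count (an assumption), the module runs from 31 to 30 + 35 = 65.

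**Step 2: could the module be numbered separately?** On the same assumption, a separately numbered module would run from 1 to 35, and the printed swallowing item 38 would not exist. Continuous numbering fits all the module numbers printed.

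**Step 3: place the two global health items.** Item 29 lies within 1 to 30. Item 40 does not. Since 40 − 30 = 10, it would be the tenth module item, after every number listed for pain (31 to 34) and swallowing (35, 38). One of the two listed items is therefore not in the named instrument.

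**Step 4: what was probably meant.** If the list has two core items and the first is 29, the second can only be 30, because no other core number follows 29. This is an inference, since the documents do not otherwise list the scale's items.

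**Step 5: endpoints affected.** Section 4.2 has four patient-reported secondary comparisons: time to deterioration in global health, in pain and in swallowing, and mean change in global health. The faulty list bears on the first and the last, so 2 of 4.

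**Step 6: the swallowing list.** Pain is written with *to*, and swallowing with *and*. Section 9.2.2 names pain first and swallowing second among the module's multi-item scales, which would fit consecutive runs of 31 to 34 and 35 to 38. However, no section says how many items the swallowing scale has, and two items would satisfy the term multi-item. The contrast is a reason to check, not a demonstrated error.

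Section 9.2.2 also says "Each of the multi-item scales includes a different set of items" and "no item occurs in more than one scale". Those words describe the scales within the QLQ-C30 and do not help to locate item 40.

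**The case against.** The strongest reply is that the bracketed numbers are an aside. Sections 4.2 and 9.2.2, the synopsis, and the endpoint definitions in Section 11.9.3 itself all identify the scale by name and instrument, and Section 9.2.2 describes both questionnaires as validated. An analyst working from the scoring manual would probably score the scale correctly and treat 40 as a misprint. This stands, and it is why the point is a text error and not a prediction that the endpoints would be mis-scored.

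A reader might go further in three ways, none of which the documents support:

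- **That the global health score would mix items running in opposite directions.** Section 9.2.2 says that higher is better for global health and worse for symptom scales and items, but no section says what item 40 measures.
- **That the swallowing score drops half of a four-item scale.** The four-item run is inferred from the numbering pattern only.
- **That three of the four patient-reported secondary endpoints are affected.** That count depends on the swallowing inference. The documents establish two.

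It is also fair to say that nothing is at risk in practice. With one patient treated and only listings planned, neither endpoint will be compared between arms. That limits the consequence but leaves the protocol text wrong.

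**Conclusion.** The item list for the global health scale in Section 11.9.3 is wrong as written: one of its two numbers cannot belong to a 30-item core. If followed literally it would mis-score two secondary endpoints. It is very likely a typographical slip, because the scale is named correctly throughout.

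The conclusion rests on the core having 30 items, which follows from its name and from the module numbering starting at 31. That 30 was intended is a presumption. The swallowing list is an open question only. No sample size, power, alpha or primary endpoint is affected, and the current SAP contains no derivation that carries the error.

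**What to change.** In Section 11.9.3, correct the global health item list against the instrument's scoring manual (presumably items 29 and 30), and add a sentence that all QLQ-C30 and H&N35 scores follow that manual. In the same edit, check the swallowing list against the manual and write it as a range only if the manual says so. An equally sound alternative is to delete the item numbers and rely on the scale names together with the manual.

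The current SAP needs no change. Any separate scoring specification that copied these lists should be checked. The cost is a small text correction with no effect on conduct or data collection. As the trial has been discontinued, a documented correction or note to file would be enough, and it would keep the error out of later protocols that reuse the text.

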1.2 Schedule of Events

Table 1: Schedule of Events (Excluding Pharmacokinetic, Immunogenicity, ██████████ Sampling)

Procedure / Period:	Screening	Treatment Cycles (3-Week Cycles)					Post-treatment		
		Cycle 1 Only			Cycle 2 and Beyond		Follow-up Visit 1 y	Follow-up Visit 2 y	Survival Follow-up z
Study Days a :	Day -28 to -1	Day 1	Day 3 (- 1 day)	Phase 3 only: Day 5 (± 1 day)	Day 1 (± 3 days)	Day 3 (+ 2 days)	30 days from last dose (± 7 days)	90 days from last dose (± 7 days)	Every 12 weeks (± 14 days)
Informed consent	X								
Inclusion/ exclusion criteria	X								
Demographics and medical history b	X								
Tumor biopsy c	X								
Randomization		X d							
Physical examination e	X	Predose			Predose		X	X	
Vital signs f	X	X f	X		X f		X	X	
ECOG performance status g	X	Predose			Predose		X	X	
ECG h	X								
ECHO/MUGA i	X								
Pregnancy test j	X j	Predose j			Predose		X	X	
Hematology and serum chemistry k	X	Predose			Predose		X		
Coagulation k	X								
Thyroid function tests (T3 [total or free], free T4, TSH) l	X				Predose l		X		

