**Arm A (bempegaldesleukin plus pembrolizumab) only:**

- r. See [Appendix 1B](#) for the list of local laboratory tests that require evaluation within 24 hours prior to bempegaldesleukin administration or as soon as locally feasible.
- s. Hydration guidelines provided in [Section 6.2.3.2](#).
- t. See [Section 6.7.1](#) for premedication guidance before study drug infusion(s).
- u. In Cycles 1 and 2, site personnel must contact the patient (by telephone or clinic visit) once between Days 3 and 5 (inclusive) following infusion, to remind the patient of the oral hydration guidelines, to assess for any symptomatology and compliance with the guidelines, and document the results of the discussion (see [Section 6.2.3.2](#)). In Cycles 3 and beyond, the oral hydration follow-up is conducted as clinically indicated for patients in Arm A receiving bempegaldesleukin and pembrolizumab.
- v. Within 5 calendar days following randomization, the patient should receive the first dose of study treatment. Study drug infusion timing should be as close to 30 minutes as possible; however, a window between -5 minutes and +10 minutes is permitted (ie, infusion time is 30 minutes -5 min/+10 min). See [Sections 6.2.2.1](#) and [6.2.2.2](#) for additional details.
- w. At each visit specified, health-related quality of life assessments should be performed in the following order: EQ-5D first, then European Organization for the Research and Treatment of Cancer Quality of Life Questionnaire Core 30 (EORTC QLQ-C30), and finally the EORTC Quality of Life Questionnaire-head and neck cancer specific module (QLQ-H&N35). The questionnaires will be completed prior to dosing at Cycle 1, Cycle 2, Cycle 3, Cycle 4 and every 2 cycles thereafter (eg, Cycle 6, Cycle 8, Cycle 10) up to 1 year from treatment initiation or End of Treatment, whichever occurs first, and at the Follow-up Visit 1. See [Section 9.2](#).
- x. Additional subsequent cancer therapy details such as regimen, setting of the regimen, line of therapy, start date and end date of each regimen, best response to the regimen, and date of progression to subsequent anticancer therapies will be collected.
- y. For Follow-up visits, see [Section 6.3.1](#).
- z. For Survival Follow-up, see [Section 6.3.2](#).

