#### 6.2.4 Duration of Treatment

In the initial treatment (ie, First Course), patients may remain on treatment for up to 35 cycles (approximately 2 years) of study drug (ie, bempegaldesleukin plus pembrolizumab or pembrolizumab monotherapy). Note: the number of cycles of study medication is calculated starting with the first dose.

For patients who have attained a confirmed complete response and have received at least 2 cycles of study drug beyond the initial complete response confirmation date, treatment may be stopped.

These patients may be eligible for the Second Course as described in Section 6.2.6.

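### The primary time point for the secondary quality-of-life comparison is Week 12, but no on-treatment questionnaire is scheduled then (Week 12 is Cycle 5 Day 1, which the schedule skips).

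*Protocol*

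**What the plan says.** Protocol Section 4.2 lists this secondary objective: "To compare mean change from baseline in global health status/quality of life". Its endpoint is "Mean change from baseline in global health status/quality of life scales of EORTC QLQ-C30".

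Section 11.9.3 analyses it with a constrained longitudinal data analysis model containing an arm-by-time interaction and the stratification factors. It then fixes the time point: "Treatment effect on PRO score change from baseline will be primarily evaluated at Week 12". It adds: "The differences in the least square mean change from baseline will be reported at the primary analysis time point".

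The collection schedule is in Section 1.2, Table 1, under the heading "Treatment Cycles (3-Week Cycles". The questionnaire row shows a predose entry for Cycle 1 and for Cycle 2 onwards, both governed by footnote w: "The questionnaires will be completed prior to dosing at Cycle 1, Cycle 2, Cycle 3, Cycle 4 and every 2 cycles thereafter". The footnote continues: "eg, Cycle 6, Cycle 8, Cycle 10) up to 1 year from treatment initiation or End of Treatment", whichever comes first. It adds one form at Follow-up Visit 1. Sections 8.4 and 9.2 refer back to Section 1.2 and give no other schedule.

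The SAP contains no patient-reported outcome analysis.

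**The concern.** The time point at which the arms are to be compared is not one at which patients on treatment complete the questionnaire. If time enters the model as visit categories, there is no scheduled Week 12 level from which to estimate the named contrast.

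The analyst would then have to choose after data collection. Using Week 9, using Week 15 or pooling the two each answers a different question. Using only forms that fall near Week 12 selects patients whose dosing slipped or who stopped early. Arm A carries an additional drug with its own delay criteria (Section 6.5.1.2), so that selection could differ between arms. The trial is open-label and the outcome is self-reported, which makes an unplanned choice of time point harder to defend.

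**Working it through.** **Inputs**

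- Cycle length: 3 weeks (21 days), Table 1.
- Questionnaire cycles: 1, 2, 3, 4, 6, 8, 10 and so on, up to 1 year or end of treatment (footnote w).
- Day 1 window from Cycle 2: ± 3 days (Table 1). Minimum dosing interval: 18 days (Section 6.2.2.2).
- Follow-up Visit 1: 30 ± 7 days after the last dose (Section 6.3.1).
- First dose within 5 calendar days of randomization (Section 6.2.1).

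**Check of the cycle-to-calendar mapping.** Section 6.2.4 says "patients may remain on treatment for up to 35 cycles (approximately 2 years) of study drug". 35 × 3 = 105 weeks, and 35 × 21 / 365.25 = 2.01 years. The 17-cycle Second Course gives 17 × 3 = 51 weeks, and 17 × 21 / 365.25 = 0.98 years, against a stated figure of about 1 year. The mapping reproduces the plan's own figures.

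**Scheduled weeks.** Week of Cycle k Day 1 = 3 × (k − 1); study day = 1 + 21 × (k − 1).

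| Cycle | Week | Day | Questionnaire |
|---|---|---|---|
| 1 | 0 | 1 | yes |
| 2 | 3 | 22 | yes |
| 3 | 6 | 43 | yes |
| 4 | 9 | 64 | yes |
| **5** | **12** | **85** | **no** |
| 6 | 15 | 106 | yes |
| 8 | 21 | 148 | yes |
| 10 | 27 | 190 | yes |

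The later scheduled weeks are 33, 39, 45 and 51. Week 12 corresponds to cycle 12/3 + 1 = 5.

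**Other ways of counting, taken one at a time**

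- Fixed ± 3-day window: Cycle 4 on Days 61–67, Cycle 6 on Days 103–109.
- Every interval at 18 days or every interval at 24 days (21 + 3): Cycle 4 on Days 1 + 18 × 3 = 55 to 1 + 24 × 3 = 73; Cycle 6 on Days 1 + 18 × 5 = 91 to 1 + 24 × 5 = 121. Day 85 lies in neither range. Neither do Days 78–84, the alternative reading of Week 12.
- Weeks counted from randomization with the first dose 5 days later: Cycle 4 at (63 + 5)/7 = 9.7 weeks, Cycle 6 at (105 + 5)/7 = 15.7 weeks.
- Nearest-visit rule: 12 − 9 = 3 and 15 − 12 = 3, a tie.

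**Which forms could land near Week 12**

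- Follow-up Visit 1 after a last dose at Cycle 3: Day 43 + 30 = 73 (range 66–80), week 72/7 = 10.3.
- Follow-up Visit 1 after a last dose at Cycle 4: Day 64 + 30 = 94 (range 87–101), week 93/7 = 13.3.
- A Cycle 4 form on Day 85 needs 85 − 64 = 21 days of accumulated delay. Section 6.2.2 says dosing visits are delayed rather than skipped, so this can happen.

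The forms closest to Week 12 therefore come from early discontinuers and from patients with delayed dosing.

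**The case against.** The date arithmetic is not in dispute; the case on the other side concerns scope and wording.

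- **The model could interpolate.** Section 11.9.3 does not say whether time is categorical. With a continuous or spline term, a Week 12 contrast can be estimated from Weeks 9 and 15. In that case the comparison is underspecified rather than impossible. This is fair, but the protocol states no such function, and its references to a time point and to summaries by visit read more naturally as visit categories.
- **Follow-up Visit 1 is itself a scheduled questionnaire visit.** This is correct, so the absence of scheduled data is exact only for on-treatment forms. It does not rescue the comparison, because with nominal dosing the visit approaches Week 12 only in patients who stopped at about Cycle 3 or 4.
- **The ± 3-day window governs visits, not the assignment of forms to analysis time points.** This is also correct. The conclusion does not rest on that window, because neither document gives an analysis window.
- **An SAP might have supplied the rule.** Section 11.1 defers detailed methods to the SAP. The SAP provided was written after discontinuation and is silent on this. The finding therefore concerns the protocol text.
- **The impact is narrow.** This stands. Only the mean-change endpoint uses Week 12, the protocol assigns no alpha to the contrast, and Week 9 and Week 15 results would appear in the by-visit summaries. One patient was enrolled and only listings are planned, so no reported result is affected.

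**Conclusion.** The concern holds. The protocol's rule for when to compare the arms conflicts with its own collection schedule. None of the approximately 500 planned patients has a scheduled on-treatment questionnaire at Week 12, and the nearest scheduled forms are 3 weeks away on either side.

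This assumes that Week 12 is counted from Cycle 1 Day 1 with 3-week cycles. It survives each alternative count tried. The statement that the contrast cannot be estimated from a scheduled visit also assumes categorical time; under continuous time the result would be an unspecified interpolation. Whether delay or early stopping would differ between arms, and by how much, cannot be derived from the documents.

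This should be corrected in the plan, but it does not threaten the primary endpoints.

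**What to change.** Make one of two changes:

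1. In Section 11.9.3, replace Week 12 with a scheduled visit: Week 9 (Cycle 4 Day 1) or Week 15 (Cycle 6 Day 1). This changes one term and adds no data collection.
2. Keep Week 12 and add Cycle 5 Day 1 to footnote w. Patients on treatment already attend for dosing, so the cost is one extra questionnaire session. This endpoint needs only the QLQ-C30, but adding the full set would keep the assessment grid the same for the QLQ-C30 and QLQ-H&N35 time-to-deterioration endpoints.

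With either change, state whether time is categorical or continuous. Define the analysis windows, and say how forms from delayed cycles and from Follow-up Visit 1 are assigned. That takes a few sentences and removes the choice from the analyst once data are in hand.
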